1. SCOPE

This statistical analysis plan (SAP) describes the statistical analyses and data presentations planned for Protocol 747-302, Clinical Outcomes with OBeticholic Acid in Liver Treatment (COBALT), Version 6. It provides a detailed description of the strategy, rationale, and statistical methods to be used to meet the study objectives, as well as additional details to the statistical analyses that were described in the study protocol. Any deviations from the methods specified in this SAP will be documented in the clinical study report (CSR). If after the database lock additional analyses are required to supplement the planned analyses described in this SAP or any addendums, they will be identified as post-hoc in the CSR.

2. STUDY OBJECTIVES AND HYPOTHESES

2.1. Study Objectives

To support the primary objective, the primary efficacy endpoint has been expanded beyond what was outlined in Protocol Version 6. Further details are presented in [Section 14.1](#).

2.1.1. Primary Objective

The primary objective of this study is to compare the effect of obeticholic acid (OCA) to placebo, in conjunction with established local standard of care, on clinical outcomes in subjects with primary biliary cholangitis (PBC) as measured by time to first occurrence of the following adjudicated events, derived as a composite event endpoint (including all Group 1 – Group 3 events).

Group 1:

- Death (all-cause)
- Liver transplant
- Hospitalization (as defined by a stay of 24 hours or greater) for new onset or recurrence of:
 - Variceal bleed
 - Hepatic encephalopathy (as defined by a West Haven score of ≥ 2)
 - Spontaneous bacterial peritonitis (confirmed by diagnostic paracentesis OR presence of $>250/\text{mm}^3$ polymorph leucocytes [PMNs] in the ascitic fluid)
 - Bacterial empyema (confirmed by diagnostic thoracentesis OR presence of $>250/\text{mm}^3$ PMNs in the pleural fluid)
- Uncontrolled or refractory ascites (requiring large volume paracentesis)
- Portal hypertension syndromes:
 - Hepatorenal syndrome (as defined by International Ascites Club [[Angeli 2019](#)])
 - Portopulmonary syndrome
 - Hepatopulmonary syndrome

- Model of end-stage liver disease (MELD)-Na score ≥ 15 if MELD-Na < 12 at baseline
- MELD score ≥ 15 if MELD-Na ≥ 12 at baseline

Group 2:

- Progression to decompensated liver disease (for subjects without decompensation at baseline), prioritized as follows:
 - New onset of:
 - Hepatic hydrothorax
 - Variceal bleeding
 - Ascites requiring treatment with sodium restriction, diet modification, or diuretics
 - Hepatic encephalopathy requiring lactulose and/or rifaximin
 - New onset of:
 - Child-Pugh ≥ 7
 - Total bilirubin > 3 mg/dL

Group 3:

- Progression to clinical evidence of portal hypertension without decompensation (for subjects without decompensation or clinical evidence of portal hypertension at baseline)
 - Endoscopic evidence of portal hypertension without bleeding
 - Gastroesophageal varices (requiring banding or progression to large varices if no or small varices were observed at baseline)
 - Portal hypertensive gastropathy
 - Platelets $< 150 \times 10^9/L$ with splenomegaly and/or with transient elastography > 15 kPa

2.1.2. Secondary Objectives

- To assess the effect of OCA compared to placebo on time to first occurrence of death, liver transplant, MELD-Na score ≥ 15 if MELD-Na < 12 at baseline, MELD score ≥ 15 if MELD-Na ≥ 12 at baseline, uncontrolled or refractory ascites, portal hypertension syndromes (hepatorenal syndrome, portopulmonary syndrome, hepatopulmonary syndrome), or hospitalization for new onset or recurrence of variceal bleed, hepatic encephalopathy, spontaneous bacterial peritonitis, or bacterial empyema.
- To assess the effect of OCA compared to placebo on time to first occurrence of death, liver transplant, MELD ≥ 15 , uncontrolled ascites, or hospitalization for new onset or recurrence of variceal bleed, hepatic encephalopathy, or spontaneous bacterial peritonitis.

- To assess the effect of OCA compared to placebo on time to first occurrence of each individual component of the primary endpoint as listed above.
- To assess the effect of OCA compared to placebo on time to occurrence of liver-related death.
- To assess the effect of OCA compared to placebo on progression to cirrhosis.
- To assess the effect of OCA compared to placebo on time to occurrence of hepatocellular carcinoma (HCC).
- To assess the effect of OCA compared to placebo on disease progression via the following:
 - Liver biochemistry
 - Markers of inflammation and fibrosis
- To characterize the PK of OCA and its conjugates in a subset of subjects.
- To assess health outcomes and pharmacoeconomics including cost-effectiveness, resource utilization, and quality of life measures in subjects treated with OCA compared to placebo.
- To assess the safety and tolerability in subjects treated with OCA compared to placebo.

2.2. Hypotheses

2.2.1. Primary Hypothesis

The study is intended to assess whether there is a difference between OCA and placebo in the time from baseline to the first occurrence of the composite event endpoint (as defined in [Section 2.1.1](#), Groups 1 – 3).

Two-sided hypotheses are expressed in terms of:

- The null hypotheses (H_0) that the two hazard rates (h_{OCA} , $h_{Placebo}$) are the same, that is, that there is no difference between the OCA and placebo populations in the probability of an event at any timepoint.
- The alternative hypothesis (H_1) that the two hazard rates are not the same ($h_{OCA} \neq h_{Placebo}$)

2.2.2. Secondary Hypothesis

The secondary hypotheses are intended to assess whether there is a difference between OCA and placebo in the time from baseline to the first occurrence of the composite event endpoint (as defined in [Section 2.1.1](#)) and other time-to-event endpoints.

Two-sided hypotheses are expressed in terms of:

- The null hypotheses (H_0) that the two hazard rates (h_{OCA} , $h_{Placebo}$) are the same, that is, that there is no difference between the OCA and placebo populations in the probability of an event at any timepoint.
- The alternative hypothesis (H_1) that the two hazard rates are not the same ($h_{OCA} \neq h_{Placebo}$)

3. SUMMARY OF STUDY DESIGN

[figure not shown]
This Phase 4, double-blind, randomized, placebo-control, multicenter study will evaluate the effect of OCA on clinical outcomes in subjects with PBC who are at higher risk of liver-related clinical complications.

Eligible subjects will have a diagnosis of PBC with bilirubin levels $>ULN$ and $\leq 5x ULN$ and/ or $ALP > 3x ULN$. Subjects will be screened twice during a 1- to 8-week Screening period prior to entering the study to allow for the collection of repeat serum chemistry samples (at least 2 weeks apart) to confirm pretreatment alkaline phosphatase (ALP) and total bilirubin values.

Investigational product (IP) will be taken orally, once daily for the majority of subjects; dose and frequency will be modified for subjects with cirrhosis (including subjects progressing to cirrhosis during the study) and classified as Child-Pugh B or C. The randomization will be stratified by ursodeoxycholic acid (UDCA) treatment (yes/ no) and baseline bilirubin categories ($>$ upper limit of normal [ULN]/ $\leq ULN$). A minimum of 30% of subjects will have elevated bilirubin ($>ULN$) at Screening.

The study is event driven and will continue until approximately 127 adjudicated primary endpoint events have been accrued in unique subjects, or until the Sponsor (eg, based on a recommendation from the Data Monitoring Committee (DMC)) terminates the study. Subjects are expected to be followed for a minimum of approximately 6 years. Figure 1 below displays the study design diagram. Schedules of study procedures are outlined in Table 1 (Screening to Month 12) and Table 2 (Year 2 to End-of-Study Endpoints) of the study protocol, where more details are provided.

Figure 1: Schematic Diagram Study 747-302

EOS = end of study; M = month, OCA = obeticholic acid; ULN = upper limit of normal
 Initial dose titration of investigational product should occur at the Month 3 visit, or any study visit thereafter for subjects on all dosing regimens, based on tolerability and biochemical response (Up-titration should be considered when ALP and/ or total bilirubin are $>ULN$). Subsequent dose titration(s) for subjects classified as Child Pugh B or Child-Pugh C and following a modified dosing schedule may occur no earlier than 6 weeks after the previous dose titration.

Dosing frequency will be determined by the presence or absence of cirrhosis and, if cirrhosis is present, by Child-Pugh Score as described below:

	Planned Dosing Regimen	
	Standard	Modified
	Noncirrhotic/ Child-Pugh A	Child-Pugh B or Child-Pugh C
Starting Dose ^a (Day 0)	5 mg daily	5 mg once weekly
Titration 1 ^b (≥Month 3)	10 mg daily	5 mg twice weekly
Titration 2 ^b (≥6 weeks after Titration 1)	NA	10 mg twice weekly

^a Starting dose based on subject's cirrhosis status and Child-Pugh Score at Screening.

^b Planned titration regimen is shown; however, the titration of dose and/or frequency is dependent on subject tolerability, biochemical response, and/or changes in cirrhosis status or Child-Pugh Score at any time during the study

^c Dosing per the twice weekly schedule must be at least 3 days apart.

With the exception of liver transplant, if a subject experiences a suspected or confirmed clinical outcomes event, the subject should continue the regular visit schedule and continue taking IP as long as the subject has not met any of the criteria for discontinuation outlined in the protocol. Subjects who discontinue IP are expected to be followed through to study closure (or at the discretion of the Sponsor).

3.1. Randomization and Blinding

This study will be conducted in a double-blind, placebo-controlled manner. Allocation to one of two treatment groups (OCA or placebo) will occur on a 1:1 ratio across sites and will be stratified by UDCA treatment (yes/no) and mean baseline bilirubin categories (>ULN/≤ULN), as specified by the central laboratory. The randomization will be based on a predefined randomization code (generated by the Sponsor or designee) using an interactive web response system (IWRS). The IWRS will also serve as an investigational product inventory and management system and may be integrated with the study database.

The unblinded data access during DMC and interim analysis is described in Safety Review Committee Charter.

3.2. Sample Size Determination

The following assumptions were used in the Protocol Version 6 sample size calculations:

- Exponential survival curves, placebo survival estimate of 0.6 at 8 years with a hazard ratio of 0.60, and total study duration of 10 years (from first subject enrolled), allowing for 4 years of subject accrual and 6 years of follow up.
- Subjects will be randomized in a 1:1 ratio to placebo or OCA.
- The 2 treatment groups will be compared using a 2-sided log rank test at the 5% level of significance.
- Two interim analyses and one final analysis are planned, with interim analyses occurring after the accrual of 50% and 75% of clinical outcome events, respectively.
- A dropout rate of 10% is assumed

Based on the randomization ratio, significance level, and assumed hazard ratio, a total of 127 events (both groups combined) was to provide 80% power to demonstrate a statistically significant difference between OCA and placebo on time to liver-related outcomes, including all-cause mortality.

In addition, based on the remaining assumptions stated above, it was estimated that approximately 428 subjects would be enrolled to attain 127 events.

Sample size calculations were based on the following composite endpoint: time to first occurrence of death, liver transplant, MELD ≥ 15 , uncontrolled ascites, or hospitalization for new onset or recurrence of variceal bleed, hepatic encephalopathy, or spontaneous bacterial peritonitis.

Due to enrollment challenges and difficulties to keep patients in the study, the trial will be terminated early by sponsor. To better evaluate the benefit-risk ratio, the composite endpoint will be revised to include additional components that occur earlier in the progression of PBC

4. ANALYSIS POPULATIONS AND APPROACHES TO ANALYSIS

4.1. Intent-to-Treat (ITT) Population

The ITT Population includes all randomized subjects who receive any amount of investigational product (OCA or placebo). The ITT Population will be the primary population used for efficacy analyses. Treatment assignment will be based on the randomized treatment.

4.2. Per Protocol (PP) Population

The PP Population includes ITT subjects who do not have any major protocol deviations that potentially affect the primary efficacy conclusion. Major protocol deviations that exclude subjects from the PP population are:

- Subject randomized into the study despite not meeting inclusion criteria or meeting exclusion criteria.
- Potential overdose, i.e. investigational product compliance $>120\%$, unless there's clear documentation.
- Subject met protocol criteria for down-titration, but dose was not adjusted.
- Prohibited change in concomitant medication whilst actively on the study, including commercial OCA.
- SAE not reported or not reported in required timeframe.
- Failure to submit local subject level safety events per IRB/EC policy.
- Withdraw criteria met, but subject not discontinued.

The PP Population will be used for the sensitivity analyses of the primary and key secondary efficacy endpoints. Treatment assignment will be based on the randomized treatment. PP patients list will be determined prior to unblinding.

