8.1.2. Sensitivity Analyses

The following sensitivity analyses will be carried out on the primary endpoint, with different population, strategy to handle the intercurrent events, or summary.

No.	Population	Strategies to address intercurrent events	Population-level summary
1	Subset of primary population, who had no major protocol violations.	Same as primary analysis	Same as primary analysis
2	Same as primary analysis	Same as primary analysis	The 2 treatment groups will be compared using the win ratio (Pocock 2012) using the unmatched method within the bilirubin randomization strata. The 95% confidence interval will be calculated using a bootstrapping method and a p-value will be calculated using the stratified Finkelstein-Schoenfeld test (Finkelstein 1999).
3	Same as primary analysis	Data collected after the intercurrent events to be excluded (while on treatment policy)	For subjects who didn't experience an event before the intercurrent event, multiple imputation will be carried out for time to event based on the available data after the intercurrent event. Details is included in the appendix.
4	Same as primary analysis	Exclude data after 90 days after a patient discontinues IP.	Same as primary analysis.
5	Same as primary analysis	Include only data prior to when a patient starts commercial OCALIVA.	Same as primary analysis.
6	Same as primary analysis	Include only data prior to when OCA was commercially available in the subject's country.	Same as primary analysis.
7	Same as primary analysis	Hypothetical strategy, ie, as if the intercurrent events didn't happen.	Hazard ratio and 95% CI will be estimated using a weighted Cox regression model with Sandwich estimator. The derivation of the weights based on Inverse Probability of Censoring Weighting (IPCW) is detailed in the appendix.

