9.2.2. Serious Adverse Events (SAE)

An AE is considered “serious” if, in the view of either the Investigator or Sponsor, it results in any of the following outcomes:

- Death
- Is immediately life threatening
- Requires in-subject hospitalization or prolongation of existing hospitalization
- Results in persistent or significant disability or incapacity
- Results in a congenital abnormality or birth defect
- Is an important medical event that may jeopardize the subject or may require medical intervention to prevent one of the outcomes listed above

Events not considered to be SAEs are hospitalizations for:

- Routine monitoring of the studied indication and not associated with any deterioration in condition or AE
- Elective treatment for a pre-existing condition that did not worsen

- Respite care or observation when there is no AE associated with the hospitalization

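### The per-protocol population excludes subjects for failures in safety reporting, which selects on outcome and discards valid endpoint events from supportive analyses

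*SAP*

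**What the plan says.** SAP Section 4.2 defines the PP population as "ITT subjects who do not have any major protocol deviations that potentially affect the primary efficacy conclusion". A list of excluding deviations follows. Most items concern eligibility, dosing, prohibited medication or withdrawal criteria. Two concern safety reporting: "SAE not reported or not reported in required timeframe" and "Failure to submit local subject level safety events per IRB/EC policy". Neither carries an exception for subjects whose endpoint event is known and adjudicated.

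The section gives the use of the population: "The PP Population will be used for the sensitivity analyses of the primary and key secondary efficacy endpoints". In Section 8.1.2 it appears as sensitivity analysis 1, worded as "Subset of primary population, who had no major protocol violations". Section 8.2.2 applies it to the key secondary time-to-event endpoints. The one safeguard stated is "PP patients list will be determined prior to unblinding".

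**The concern.** A PP population should remove subjects whose course no longer reflects the treatment comparison that the protocol intended. A late or missing safety report is a failure of site conduct. It does not change who was eligible or what the subject took. Nor does it move the endpoint date: Appendix A counts time to the occurrence of the event, not to its report, and Section 8.1.1 admits only adjudicated events.

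The two items also depend on what happens after randomization. A subject with no safety event cannot breach them, and a subject with several has several chances to do so. Those events overlap with the endpoint, so the exclusion acts on the outcome being analysed. At stake are the event count, and possibly the hazard ratio, in analyses meant to show that the ITT result is robust.

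**Working it through.** **Overlap between SAE and endpoint**

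- Section 9.2.2 makes death a serious criterion, and also "Requires in-subject hospitalization or prolongation of existing hospitalization". Its carve-outs cover routine monitoring, elective treatment and respite care only.
- Section 9.2 counts worsening of the underlying disease as an adverse event.
- Section 2.1.1 makes all-cause death, and hospitalization of 24 hours or more for listed liver complications, components of the primary endpoint.
- So one occurrence can be both an SAE and an endpoint event, and one late report on it removes the subject and the event.

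**Where the PP analysis stands alone**

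Section 8.2 lists three key secondary endpoints. The second, which is primary for the EMA filing, receives all the Section 8.1.2 analyses except the win ratio. For the other two, the Group 1 composite and time to transplant or death, Section 8.2.2 names only the PP analysis.

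**Design figures, as a check on the inputs**

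Section 3.2 gives HR 0.60, two-sided 5%, 80% power, placebo survival 0.6 at 8 years, 4 years of accrual within 10 years, and 10% dropout.

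- Freedman events: (1.960 + 0.842)² × ((1 + 0.6)/(1 − 0.6))² = 7.849 × 16 = 125.6, or 126 against 127 stated.
- Subjects: with placebo hazard −ln(0.6)/8 and uniform accrual, 127 events need 384 subjects; 384/0.90 = 427 against about 428 stated.

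The inputs reproduce. The plan has no figure for the PP population itself.

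**Events lost**

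The documents give no count of late or unreported SAEs, so assume that a share q of subjects with an endpoint event is dropped. The only event count available is 84, on the Protocol Version 6 endpoint at the early stop (Section 14.1). Events left are 84 × (1 − q), and the standard error of the log HR grows by 1/√(1 − q). Power uses the Schoenfeld formula at HR 0.60 and two-sided 0.041, only as a gauge of information.

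| q | Events left of 84 | SE multiplied by | Power |
|---|---|---|---|
| 0 | 84 | 1.00 | 0.62 |
| 5% | 80 | 1.03 | 0.59 |
| 10% | 76 | 1.05 | 0.57 |
| 20% | 67 | 1.12 | 0.52 |

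**Effect on the hazard ratio**

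Dropping a share of event subjects scales an arm's event rate by about (1 − q), so the HR is multiplied by about (1 − q_OCA)/(1 − q_placebo). A Cox simulation with 200,000 subjects, the design placebo hazard and censoring uniform between 6 and 10 years gave the following.

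| True HR | q OCA / q placebo | HR, all subjects | HR, after exclusion |
|---|---|---|---|
| 1.0 | 10% / 10% | 1.00 | 1.01 |
| 1.0 | 20% / 20% | 0.98 | 0.98 |
| 1.0 | 15% / 5% | 0.99 | 0.91 |
| 1.0 | 30% / 10% | 0.99 | 0.81 |
| 1.0 | 10% / 30% | 1.00 | 1.22 |
| 0.6 | 20% / 20% | 0.59 | 0.58 |
| 0.6 | 30% / 10% | 0.60 | 0.47 |
| 0.6 | 10% / 30% | 0.60 | 0.72 |

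With equal shares the HR barely moves. With unequal shares it moves in the direction of the simple ratio, which somewhat overstates the size: 0.70/0.90 = 0.78, against 0.81 simulated.

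**The case against.** Several points on the other side stand.

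- The primary and key secondary tests use the ITT population, and the testing hierarchy in Section 8.6 does not depend on PP. The primary endpoint has six other sensitivity analyses.
- The overlap is partial. MELD or MELD-Na ≥15, Child-Pugh ≥7, bilirubin above 3 mg/dL and the platelet or elastography criterion need not be SAEs.
- The protocol is not at hand and might exempt endpoint events from SAE reporting. The SAP states no exemption, and selection through other SAEs would remain.
- An SAE never reported might be a missed endpoint event, which does bear on ascertainment. That is a reason to adjudicate the event; it does not justify dropping a subject whose event is known and dated.

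Fixing the list before unblinding prevents choice by arm but does not undo selection on outcome.

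A reader might go further and infer that any difference in SAE frequency between arms biases the PP hazard ratio. The documents do not support this. What matters is the share of event subjects dropped in each arm; fewer SAEs because the drug prevents events would not by itself shift the HR. Nothing in this double-blind plan shows that late reporting differs by arm.

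A reader might also put a multiple on how much more often event subjects are lost than event-free ones. Such a figure follows from the SAE counts assumed. With 10% of SAEs late, 2 against 0.5 SAEs per subject gives 19% against 5%, a ratio of about 3.7; 1 against 0.5 gives 10% against 5%, about 2. The SAP supplies no such counts.

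**Conclusion.** The two items do not meet the test that Section 4.2 sets for itself: they are not "major protocol deviations that potentially affect the primary efficacy conclusion". As written they select on a post-randomization outcome and remove valid adjudicated events from supportive analyses. The direct consequence is loss of events and precision, of unknown and possibly small size. The fall from 84 events to between 80 and 67 rests on an assumed 5% to 20% loss and applies to the Protocol Version 6 endpoint; no event count is given for the expanded primary endpoint. Bias in the hazard ratio is possible but conditional on unequal loss between arms, and neither its size nor its direction can be read from the documents. No confirmatory conclusion changes. The point deserves correction because PP is the only sensitivity analysis for two key secondary endpoints. One of these is transplant or death, where every death meets an SAE criterion.

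**What to change.** Before the PP list is fixed, delete the two safety-reporting items from the exclusion list in Section 4.2 and leave the other items as they are. Summarize and list these deviations under Section 5.1, which already provides for that. Add one sentence: if an unreported SAE raises doubt about endpoint ascertainment, the event goes to adjudication and the subject stays in the PP population. The cost is a few lines of SAP wording; no data are lost and no other analysis changes.
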